4 ENDPOINTS

4.1 Efficacy Endpoints

4.1.1 Disease Free Survival

DFS is the primary endpoint.

Disease-Free Survival is time between randomization date and first date of recurrence or death, whichever occurs first. Recurrence is defined as the appearance of one or more new lesions, which can be local, regional, or distant in location from the primary resected site (by imaging or pathology). DFS will be programmatically determined based on the disease recurrence date provided by the investigator. For subjects who remain alive and without recurrence, DFS will be censored on the date of last evaluable disease assessment. The on-study disease assessment considers CT scan, MRI and biopsy

Detailed censoring rules for the primary definition of DFS are presented in Table 4.1.1-1; graphical display is presented in [Figure 2](#).

Table 4.1.1-1: Censoring Scheme Used in the Primary Definition of DFS

[figure not shown]
Situation	Date of Event or Censoring	Outcome
Recurrence (a) (c) (d) (e)	Date of first recurrence	Event
Death (b) (c) (d) without recurrence	Date of death	Event
No baseline disease assessment	Date of randomization	Censored
No on-study disease assessments and no death (d)	Date of randomization	Censored
Death with prior subsequent therapies or second non-esophageal and non-GEJ primary cancer (d)	Date of randomization	Censored
No recurrence and no death (d) (e)	Date of last evaluable disease assessment	Censored
New anticancer therapy, tumor-directed radiotherapy, or tumor-directed surgery received or the second non-esophageal and non-GEJ primary cancer date without recurrence or death reported prior to or on the same day of disease assessment (d) (e)	Date of last evaluable disease assessment prior to or on the same date of initiation of subsequent therapy or the second non-esophageal and non-GEJ primary cancer date whichever is earlier	Censored

Table 4.1.1-1: Censoring Scheme Used in the Primary Definition of DFS

(a) recurrence = appearance of one or more new lesions, which can be local, regional, or distant in location from the primary resected site
(b) All deaths will be included as DFS event - regardless of cause or of how long it has been since the last known disease evaluation.
(c) Without receiving preceding new anticancer therapy, tumor-directed radiotherapy, tumor-directed surgery, or second non-esophageal and non-GEJ primary cancer.
(d) Without baseline disease.
(e) With on-study disease assessment.

Per protocol inclusion criteria, subjects must have complete resection (R0), have been surgically rendered free of disease. Should a subjects not be disease-free by imaging at study entrance, this will be considered as a relevant protocol deviation per [section 7.2](#) of this SAP. A subject with disease at baseline is considered as having a DFS event at randomization.

Figure 2: Graphic Display of DFS Primary Definition

* Second non-esophageal and non-GEJ primary cancer; A subject with disease at baseline is considered as having a DFS event at randomization.

DFS per BICR

For this study, all radiologic imaging will be transmitted to a centralized imaging core lab for storage by an independent review committee (BICR). These images will be read upon request, in which case DFS by BICR will also be derived.

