8.3 Endpoints

8.3.1 Primary Endpoint

Disease-free survival is the primary endpoint of this study. Disease-free survival is the time between randomization date and first date of recurrence or death, whichever occurs first. Recurrence is defined as the appearance of one or more new lesions, which can be local, regional, or distant in location from the primary resected site (by imaging or pathology). DFS will be programmatically determined based on the disease recurrence date provided by the investigator. All deaths without prior recurrence will be included as DFS event - regardless of cause or of how long it has been since the last known disease evaluation. For subjects who remain alive and without recurrence, DFS will be censored on the date of last evaluable disease assessment.

Detailed censoring rules for the primary definition of DFS are presented in Table 8.3.1-1. (Sensitivity analyses of DFS will be described in the Statistical Analysis Plan [SAP]).

Table 8.3.1-1: Censoring Scheme Used in the Primary Definition of DFS

Situation	Date of Event or Censoring	Outcome
Recurrence ^{a,c}	Date of first recurrence	Event
Death ^{b,c} without recurrence	Date of death	Event
No baseline disease assessment	Date of randomization	Censored
No on-study disease assessments and no death	Date of randomization	Censored
No recurrence and no death	Date of last evaluable disease assessment	Censored
New anticancer therapy, tumor-directed radiotherapy, or tumor-directed surgery received without recurrence reported prior to or on the same day of disease assessment	Date of last evaluable disease assessment prior to or on the same date of initiation of subsequent therapy	Censored
Second non-esophageal and non-GEJ primary cancer reported prior to or on the same day of disease assessment	Date of last evaluable disease assessment prior to or on the same date of diagnosis of second non-esophageal and non-GEJ primary cancer	Censored

^a recurrence = appearance of one or more new lesions, which can be local, regional, or distant in location from the primary resected site

^b All deaths will be included as DFS event - regardless of cause or of how long it has been since the last known disease evaluation.

^c Without receiving preceding new anticancer therapy, tumor-directed radiotherapy, or tumor-directed surgery

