7.5.2 Primary Efficacy Endpoint

DFS will be compared between treatment arms using a two-sided log rank test, stratified by the three randomization stratification factors as recorded in IWRS.

The HR for DFS with its corresponding two-sided $100 \times (1 - \text{adjusted } \alpha)\%$ CI will be estimated via a stratified Cox model with treatment arm as the only covariate in the model. Adjustment on the CI will be based on the reallocated alpha level.

DFS for each treatment arm will be estimated and plotted using the KM product-limit method. Median survival time will be computed using the KM estimate and a 95% CI for the median will be computed based on a log-log transformation of the survivor function.

Source of DFS Event

The source of DFS event will be summarized by treatment group:

- Recurrence (local recurrence, regional recurrence, distant recurrence)
- Death

Status of Censored Subjects

The status of subjects who are censored in the DFS KM analysis will be tabulated for each randomized treatment group using the following categories:

- 1) Censored on randomization date
 - a) no baseline disease assessment
 - b) no on-study disease assessment and no death
 - c) no on-study disease assessment but death with prior subsequent therapy or second primary cancer
- 2) Censored on date of last evaluable disease assessment on-study
 - a) Received subsequent anti-cancer therapy
 - b) Second non-esophageal and non-GEJ primary cancer
 - c) Still on treatment
 - d) In follow-up
 - e) Off study
 - i) lost to follow-up
 - ii) subject withdrew consent
 - iii) other

DFS rates at fixed time points (e.g. 6 months, depending on the minimum follow-up) will be presented along with their associated 95% CIs. These estimates will be derived from the Kaplan-Meier estimate and corresponding CIs will be derived based on Greenwood formula for variance derivation and on log-log transformation applied on the survivor function.

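### SAP Table 4.1.1-1 censors deaths after new therapy or a second primary at randomization without limiting the row to unscanned subjects, contrary to SAP 7.5.2

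*SAP*

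**What the plan says.** SAP 4.1.1 presents Table 4.1.1-1 as the detailed censoring rules for the primary definition of DFS. Two of its rows matter here.

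- The row "Death with prior subsequent therapies or second non-esophageal and non-GEJ primary cancer (d" (the closing letter is its only footnote mark) is censored at randomization. Footnote (d) means that the subject had no disease at baseline.
- The last row covers new anticancer therapy, tumor-directed radiotherapy or surgery, or a second primary. It carries footnotes (d) and (e), and (e) reads "With on-study disease assessment". It censors at the "Date of last evaluable disease assessment prior to or on the same date of initiation of subsequent therapy", or the second-primary date if earlier.

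SAP 7.5.2 lists the censoring categories to be tabulated. Under randomization-date censoring, category 1c is "no on-study disease assessment but death with prior subsequent therapy or second primary cancer". Category 2, "Censored on date of last evaluable disease assessment on-study", contains 2a (subsequent anti-cancer therapy) and 2b (second primary).

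Protocol Table 8.3.1-1 has a row for new therapy "received without recurrence reported prior to or on the same day of disease assessment", which censors at the last evaluable assessment. It has no row that censors deaths after new therapy at randomization.

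**The concern.** Take a subject with clean scans to month 18 who then starts new therapy without recurrence. If alive at the DFS interim analysis, the subject falls in the last row and is censored at month 18. If dead by the DFS final analysis, the subject also meets the wording of the death row and may be censored at day 0. The censoring date then depends on something that happens after it, and 18 months of observed event-free follow-up leave the risk sets.

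This is the stated rule for the sole primary endpoint. A programmer working from the table could implement it differently from one working from 7.5.2.

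**Working it through.** **1. Does anything in the table supply the missing limit?** The row directly above, for subjects with no on-study assessment and no death, states the limit in words. The disputed row does not. The limit cannot be inferred from the absence of (e): the row that counts death without recurrence as an event also lacks (e), and it applies whether or not the subject was scanned. The table text gives no order of precedence between rows.

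**2. Side by side, for a scanned, recurrence-free subject who starts new therapy and later dies**

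| Source | Censoring date |
|---|---|
| SAP Table 4.1.1-1, death row, read literally | Randomization |
| SAP Table 4.1.1-1, last row | Last evaluable assessment |
| SAP 7.5.2, category 2a | Last evaluable assessment |
| Protocol Table 8.3.1-1, new-therapy row | Last evaluable assessment |

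SAP 7.5.2 says "The status of subjects who are censored in the DFS KM analysis will be tabulated for each randomized treatment group using the following categories". A scanned subject censored at day 0 fits none of 1a to 1c, so the planned tabulation cannot hold that subject.

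**3. Second primaries.** SAP footnote (c) removes from the event rows any death preceded by "tumor-directed surgery, or second non-esophageal and non-GEJ primary cancer". Protocol footnote c does not list second primaries, so the protocol is itself unclear for them. The protocol conflict is claimed for new anticancer therapy only.

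**4. Event counts.** SAP footnote (c) keeps these deaths from being events under either reading. Subjects who recur before any new therapy or second primary remain events under the recurrence row. Only the risk sets move.

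**5. Design figures as a benchmark.** No design figure is disputed. With 440 events, HR 0.72, 2:1 allocation and two-sided alpha 0.05 (SAP 5.3):

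- z = |ln 0.72| × √(440 × 2/9) − 1.96 = 0.3285 × 9.888 − 1.96 = 1.29, so power is 0.901 against the stated approximately 91%.
- SE(log HR) = 1/√(440 × 2/9) = 1/9.888 = 0.101.

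**6. Size of the effect.** The documents give no frequency, so rates are assumed. There were 1,000 simulated trials per scenario.

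- From the SAP: 760 subjects at 2:1 (507 and 253), Table 5.1-1 piecewise hazards, 36-month accrual (taken as uniform), cut-off at 58 months.
- Assumed: new therapy or second primary at a constant rate, independent of DFS time; death after it with a median of 6, 12 or 24 months; scans every 12 weeks for 8 scans, then every 9 months (within the planned 6 to 12); unstratified Cox model.
- Affected: new therapy or second primary before recurrence, at least one scan, dead by cut-off.
- HR ratio = HR with day-0 censoring ÷ HR with last-scan censoring. Ranges run over the three medians; Monte Carlo error is 0.0005 or less.

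| Monthly rate, nivolumab / placebo | Affected, nivolumab / placebo | HR ratio |
|---|---|---|
| Equal: 0.1%, 0.2% or 0.4% | about 1% to 7% of each arm | 1.001 to 1.006 |
| 0.1% / 0.2% | 1.0–1.9% / 1.7–3.2% | 0.990 to 0.995 |
| 0.2% / 0.4% | 2.0–3.6% / 3.3–6.0% | 0.981 to 0.991 |
| 0.2% / 0.1% | 2.0–3.6% / 0.9–1.6% | 1.007 to 1.014 |
| 0.4% / 0.2% | 3.8–7.0% / 1.7–3.1% | 1.014 to 1.029 |

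At the 12-month median, HRs (last scan, then day 0) are:

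- 0.2% in both arms: 0.709 and 0.711 (0.711/0.709 = 1.003), with 434 events under both readings.
- 0.2% / 0.4%: 0.710 and 0.700 (ratio 0.986).
- 0.4% / 0.2%: 0.714 and 0.729 (ratio 1.021).

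On the log scale the extremes are |ln 0.981| = 0.019 and ln 1.029 = 0.029, or 0.019/0.101 = 0.19 and 0.029/0.101 = 0.28 standard errors.

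At 0.2% per month in both arms, 190 to 391 of about 17,900 person-months are lost (1.1% to 2.2%), and control 12-month DFS falls by 0.4 to 0.8 percentage points.

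**The case against.** The best defence is that the intent can be recovered. The table's three rows that censor at randomization line up with 1a, 1b and 1c, and its two last-assessment rows, both marked (e), line up with category 2. The version 3.0 entry in the SAP document history records that 1c was added to 7.5.2. Read that way, the disputed row is 1c with a qualifier left out. It then fills a real gap, because the protocol table has no clear row for an unscanned subject who dies after new therapy. The last row also covers the scanned subject, so the table is ambiguous rather than plainly wrong. Figure 2 is not visible in the available copy and may show the right branch. The tabulation in 7.5.2 could expose a literal implementation, and SAP 7.5.2.1 already plans an analysis counting events and assessments on or after subsequent therapy.

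Most of this stands, and it supports the proposed wording. It does not remove the conflict. The table is where the SAP puts the detailed rules, two of its rows give different dates for the same subject, and no precedence is stated. A correct Figure 2 would still leave the table text at odds with 7.5.2. The planned sensitivity analysis does not mention second primaries and does not repair the primary definition, on which significance rests.

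The objection that the effect is small also stands. Protocol 3.4.1 prohibits antineoplastic therapy before recurrence, which limits frequency, and blinding (Protocol 4.6) limits imbalance between arms.

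**Conclusion.** The concern holds. As written, the row contradicts SAP 7.5.2 and, for new anticancer therapy, Protocol Table 8.3.1-1. The restricted rule in 7.5.2 appears to be the intended one.

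The likely numerical effect is modest: negligible with equal rates, and under a third of a standard error in the worst twofold imbalance simulated. Its direction cannot be known from the documents, because neither frequency nor split by arm is given. The simulated sizes rest on the assumed rates, times to death and scan spacing. They also assume that new therapy and second primaries arise independently of DFS time, so that last-scan censoring is non-informative by construction. The case for correction rests on the contradiction in the primary endpoint rule, not on a large expected bias.

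**What to change.** Begin the disputed row with *No on-study disease assessment, and*, keeping the rest of its wording and footnote (d). The row then matches 7.5.2 category 1c and no longer overlaps the rows marked (e), so scanned subjects follow the last row.

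Confirm that Figure 2 and the DFS programming follow the same rule. The rationale for Revised Protocol 04 says the first planned interim analysis is complete, so the check should include the derivation used there.

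Optionally, note in the SAP that its footnote (c) covers second primaries while protocol footnote c does not.

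The cost is one table row and a programming check, with no new data and no change to DFS event counts within the SAP.

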4.1.2 Overall Survival

[figure not shown]
Overall survival (OS) is defined as the time from randomization to the date of death from any cause. For subjects that are alive, their survival time will be censored at the date of last contact date (or “last known alive date”). Overall survival will be censored at the date of randomization for subjects who were randomized but had no follow-up.

4.1.3 Overall Survival Rates

Overall survival rate at 1, 2, and 3 years is defined as the probability that a subject is alive at 1, 2, and 3 years using KM method, respectively, following randomization.

Figure 3: Graphic Display of Progression-Free Survival on Subsequent Systemic Therapy

[REDACTED]

[REDACTED]

[REDACTED]

[REDACTED]

[REDACTED]

[REDACTED]

[REDACTED]

[REDACTED]

[REDACTED]

All questionnaires completed at baseline and on-study will be assigned to a time-point according

[REDACTED]

[REDACTED]

[REDACTED]

[REDACTED]

[REDACTED]

[REDACTED]	[REDACTED]
[REDACTED]	[REDACTED]
[REDACTED]	[REDACTED]
[REDACTED]	[REDACTED]
[REDACTED]	[REDACTED]
[REDACTED]	[REDACTED]
[REDACTED]	[REDACTED]
[REDACTED]	[REDACTED]
[REDACTED]	[REDACTED]

5 SAMPLE SIZE AND POWER

The sample size determination takes into consideration the comparison of the primary endpoint of DFS and the first secondary endpoint of OS between the 2 treatment arms.

5.1 Assumptions of the Control Arm

The assumptions of DFS and OS in the control arm of this study are made using the chemoradiotherapy followed by surgery (CRT + S) arm in the CROSS trial with long-term follow up (CROSS LT).⁴

Assumption for DFS

The DFS in the control arm is assumed to follow a piece-wise exponential distribution with a median of 21 months, as described below:

- The median PFS of the CRT+S arm in the CROSS LT trial was 37.7 months, which was defined from the start of CRT to disease progression.
- Considering the median time from the start of CRT+S to the completion of surgery is approximately 6 months, the median time from the completion of surgery to disease progression (to approximate DFS) is then estimated to be approximately 31 months in the setting of the CROSS LT trial.
- The study population in CA209577 are subjects who have residual pathologic disease, ie, nonpathologic complete response (non-pCR). This population represents a high-risk subgroup in the CROSS LT trial that included 29% subjects who achieved complete pathological response (pCR) after resection and 71% non-pCR subjects. This subgroup of non-pCR subjects have worse clinical outcome compared with pCR subjects.⁵ Therefore, the assumed median DFS in CA209577 should be less than 31 months.
- The assumption of 21-months median DFS in the control arm is made in consultation with external experts. Additionally, a single-center study of 518 esophageal adenocarcinoma patients suggested that 85.1% and 94.4% of relapses occurred within 24 and 36 months of surgery, respectively.⁶ This also supports the median DFS being less than 24 months in the study population.
- Chemoradiotherapy + surgery has demonstrated long-term survival benefit, as indicated by a long-lasting plateau toward the end of the survival curve in multiple clinical trials.^{7, 8} As such, the distribution of the DFS curve in the control arm of this study is assumed to follow a piece-wise exponential distribution with landmark DFS hazard rates and corresponding landmark DFS rates in [Table 5.1-1](#). The shape of the DFS curve in the control arm reflects the shape of the PFS curve in the CRT+S arm of the CROSS LT trial.

Assumption for OS

The OS in the control arm of this study is also assumed to follow a piece-wise exponential distribution with a median of 31 months. The assumption of the median OS is 10 months longer than the assumption of the median DFS in the control arm as described below:

- The median PFS and median OS of the CRT+S arm in the CROSS LT trial were 37.7 months and 48.6 months respectively, which give 11 months difference between median PFS and median OS.
- The differences between median PFS and median OS are all less than 12 months in the meta-analysis of 14 adjuvant gastric cancer studies.⁹

The shape of OS curve in the control arm of this study reflects the observed OS curve in the CRT+S arm of the CROSS LT trial. The assumed landmark OS hazard rates and corresponding landmark OS rates in this study are provided in Table 5.1-2.

Table 5.1-1: Assumed DFS Hazard Rates, Landmark Rates and Hazard Ratios

By Time	DFS Hazard Rate/DFS Rate (%) in the Control Arm	DFS Hazard Rate/DFS Rate (%) in the Nivolumab Arm	Hazard Ratio
3 months	0.035/90.0	0.035/90.0	1
1 year	0.035/65.7	0.023/73.0	0.667
2.5 years	0.03/38.3	0.02/50.9	0.667
5 years	0.02/21.0	0.013/34.1	0.667
10 years	0.003/17.5	0.002/29.5	0.8

Table 5.1-2: Assumed OS Hazard Rates, Landmark Rates and Hazard Ratios

By Time	OS Hazard Rate/OS Rate (%) in the Control Arm	OS Hazard Rate/OS Rate (%) in the Nivolumab Arm	Hazard Ratio
4 months	0.026/90.1	0.026/90.1	1
1 year	0.026/73.2	0.018/78.2	0.685
2.5 years	0.0205/50.6	0.014/60.7	0.685
6 years	0.018/23.8	0.012/36.2	0.685
12 years	0.002/20.5	0.002/32.2	0.8

5.2 Assumptions of the Treatment Effect

Assumption for DFS

An average HR of 0.72 is assumed for DFS between nivolumab and placebo in CA209577 at the final DFS analysis, which accounts for the piece-wise HRs summarized in Table 5.1-1. This translates to a median DFS of 31 months in the nivolumab arm.

In many trials studying immunotherapies, the PFS and OS curves in the immunotherapy-treated arms tend to have a delayed separation from the control arms across tumor indications;¹⁰ therefore, the treatment effect for DFS is assumed to have a delayed separation with an HR of 1 for the first 3 months and a larger treatment effect after delayed separation with an HR of 0.667. After 5 years, the treatment effect for DFS is assumed to decrease slightly with an HR of 0.8. This takes into consideration that patients who have not had disease recurrence within 5 years of surgery are generally cured from the disease and the treatment effect is more reflective of the survival benefit.

Assumption for OS

The average HR of 0.73 is assumed for OS between nivolumab and placebo in CA209577 at the final OS analysis, which accounts for the piece-wise HRs summarized in Table 5.1-2. This translates to median OS of 44 months in the nivolumab arm.

The assumption of the OS treatment effect between the 2 arms follows the same thought process as the assumption of the DFS treatment effect. The treatment effect for OS is assumed to have a delayed separation with HR of 1 for the first 4 months, and a larger treatment effect after delayed separation with an HR of 0.685. After 6 years, the treatment effect for OS is assumed to decrease slightly with an HR of 0.8. This takes into consideration the combined effect of potential for more subsequent immunotherapies in the control arm and other effective subsequent therapies in both arms for long-term survivors.

5.3 Sample Size and Power

According to the assumptions for DFS described in Sections 5.1 and 5.2, the study will require approximately 760 subjects to be randomized at a 2:1 ratio to nivolumab and placebo and observations of at least 440 DFS events in order to achieve approximately 91% power to detect an average HR of 0.72 at a 2-sided alpha of 0.05.

The sample-size determination accounts for 1 DFS interim analysis. Details of the DFS analysis timing are provided in Section 5.4.

It is estimated that these 760 subjects will be accrued and randomized within approximately 36 months from the first-patient first-visit (FPFV).

Overall survival will be tested following the overall hierarchical testing procedure¹¹ upon demonstration of superiority in DFS at either interim or final analyses for all randomized subjects.

With the sample size of 760, it is required to observe at least 460 OS events at the final OS analysis in order to achieve approximately 90% power to detect an average HR of 0.73 at a 2-sided alpha of 0.05. The power of the OS final analysis accounts for 2 OS interim analyses that occur at the same time as the DFS interim and DFS final analyses, respectively. Details of the OS analysis timing are provided in Section 5.4.

